Adverse events related to implementation of the TASKPEN pilot will be minimized through study mentors and facility-based champions who are experienced in providing integrated services. Study team members will report any unfavourable or adverse findings, especially in regard to quality of care, immediately to the MOH for consideration of remedial action. All health-related emergencies will be handled as per clinic guidelines, including management of abnormal vital signs and laboratory values identified through the patient surveys. The study QA/QC nurse and study clinical scientist/ doctor will be available to act immediately on these abnormalities, including to offer patient counselling, provide warm "handoffs" to clinical staff, refer patients for acute care at the study sites, and prescribe appropriate outpatient treatment for non-acute issues in cases where MOH staff are not available (e.g., after business hours).

No adverse events are anticipated as part of this study, as we are not testing any investigational interventions, pharmaceutical products, or medical devices. The most serious—but unlikely—adverse event would be related to inadvertent disclosure of confidential information. However, several measures

will be taken to safeguard against this risk, including the de-identification of analytical datasets, strict adherence to confidentiality procedures, and safeguarding study participant privacy at all times.

Any adverse events associated with the study will be handled by the MPIs and senior study staff and will be reported immediately to all regulatory authorities overseeing the study. We will utilize the HLB-SIMPLe project-wide Data Safety Monitoring Board (DSMB) led by the Research Coordinating Center (RCC) at Washington University in St. Louis, USA, and supported by NIH, for reporting purposes on general AEs, serious AEs (i.e., SAEs), unanticipated problems involving risks to subjects or others (UPIRSOs), protocol violations and non-compliance and social harm information. We will use the following procedures in the event of an AE, SAE, UPIRSO, protocol violation, or instance of noncompliance or social harm. In the case of any of these instances, the research team will alert the MPIs immediately (same day). Subsequently, the MPIs will report all SAEs or suspected UPIRSOs by an expedited written report sent via email to NHLBI and the DSMB chair or designee/ representative within 24hrs of the MPI's awareness of the event. The DSMB chair or representative, when necessary in conjunction with the full DSMB, will review reports and decide whether the event meets the definition of an unanticipated problem increasing risks to subjects or others. Events that meet these criteria will be considered unanticipated problems involving risks to participants or others, and will be reviewed by the convened, full DSMB. Copies of the written report will also be sent to UNZA BREC and the UNC IRB within 10 working days (with one exception) of events that meet the definition of an unanticipated problem involving risks to subjects or others. The exception is if the SAE involved death and indicates that participants or others are at increased risk of harm. In such a case, the MPIs will be required to submit a report to UNZA BREC and the UNC IRB within 3 working days. Any suspension or termination of IRB approval will include a statement of the reason(s) for the action and will be reported promptly to the NIH PO within 3 business days of receipt. In cases of protocol violations, staff re-trainings and other remedial actions will be taken by the MPIs in coordination with the RCC, CIDRZ Research Operations Department, and NIH, as appropriate.

CIDRZ holds organizational policies and procedures for the safety and security of its personnel and of the clientele with which CIDRZ employees interact during professional activities. Since the evaluation falls within the scope of CIDRZ's typical professional activities, these organizational policies and procedures will be relevant.

10. Sponsor Monitoring

The U.S. National Institutes of Health (NIH) is the primary sponsor for the study. As the sponsor, NIH may conduct monitoring or auditing of any study activity to ensure the scientific integrity of the study and to ensure the rights and protection of study participants. Monitoring and auditing activities may be conducted by any of the following individuals and parties: NIH staff ("internal"); Authorized representatives of NIH (e.g., a contracted party considered to be external"); Both internal and external parties.

Monitoring or auditing may be performed by on-site visit carried out at CIDRZ or study facilities or through other means of communications such as telephone calls or written correspondence. During the visit, any study-related materials may be reviewed and the MPIs, and other investigators, along with the study staff should be available for discussion of findings.

To ensure good clinical practice and compliance with national and international regulatory guidelines, the study may also be subject to inspection or review by authorized Zambian or international regulatory authorities, including the UNZA BREC, NHRA, UNC IRB, and UAB IRB.

11. Dissemination of Findings

All reports and publications of collected data will be presented in aggregate form only. The names or other identifiers of participating individuals will not be presented in any publication. Reports will be written so that no person may be individually identified, even indirectly. Results will be disseminated locally to the participating clinics, key stakeholders, including US government partners, and the Ministry of Health. Results from this study will also be presented at national, regional, and international meetings, and submitted to international peer-reviewed journals.

Study findings will be made available through appropriate local and international channels, including academic and public health research symposia. One or more publications will also be submitted to a peer-reviewed

12. Timeline

Milestone Plan for the TASKPEN Stu	KPEN Stu Year 1										Year 2													

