Integrated chronic care should be context specific and conducted systematically if it to be successful. WHO has provided guidance on integrating NCD management into other models of chronic care. Critical steps in the integration process include stakeholder identification and engagement, review of existing status, developments of a service delivery model, capacity building, monitoring and evaluation and review ⁴⁸.

6. Research Question

The main study question is the following: "Is it feasible, acceptable, and appropriate to task-shift the delivery of an evidence-based package of integrated cardio-metabolic health services for PLHIV within Zambia's national HIV program?"

7. Research Aims, General Objectives and Specific Objectives

The general objective of this research is to adapt WHO-PEN for a task-shifted locally-informed intervention for screening and management of cardio-metabolic co-morbidities for Zambian PLHIV, and to pilot-test it in preparation for a larger evaluation of clinical effectiveness and implementation

outcomes. To facilitate rapid formative evaluation and to initiate the stakeholder conversation on a package of integrated HIV/ NCD services for Zambia, we will begin by proposing that the five core components/ strategies from Table 2 (below) be considered for TASKPEN. To achieve this general objective, we will pursue the following specific objectives:

1. Adapt WHO PEN into a package of integrated HIV/NCD services known as "TASKPEN" and prepare TASKPEN for pilot testing in Lusaka.

- i. Conduct health facility assessments to: document current HIV infrastructure, laboratory capacity, and human resources to support integrated NCD management by NPHWs; characterize gaps in existing patient and clinic flows for optimized integrated HIV/NCD service delivery; and collect data to support pilot site identification (for objective #2).
- ii. Prepare data collection tools and methods to enable TASKPEN outcome ascertainment during pilot testing and the follow-on trial, including for the WHO quality of life data collection instrument (WHOQOL-HIV BREF) and an NCD module for the SmartCare electronic medical record.
- iii. Engage key stakeholders through formative research to: align WHO PEN algorithms to national NCD guidelines; generate feedback on proposed TASKPEN components, clinic processes and patient flows, and training materials; and obtain consensus on pilot sites (for objective #2).

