i. Adaptation of protocols, training materials, and management algorithms to the national context Review the current treatment guidelines in NCDs and other cardiometabolic diseases in Zambia and align these to the TASKPEN training materials and content, including the WHO HEARTS technical package for cardiovascular disease management in primary health care. This process will ensure consistency with MOH guidelines, culture and availability of resources of the health system. We will also ensure training materials feature an emphasis on client-centred care, which is increasingly being identified as key driver of patient retention in HIV care. Hypertension protocol: Adapt WHO PEN/ HEARTS therapy recommend based on national hypertension guidelines availability of medical supplies. Diabetes and other co-morbidities protocol: Adapt to the Zambian diabetes guidelines and practices to manage diabetes. Algorithms made suitable for NPHW to use, with guidelines when to consult or refer patient specialist physicians	Committee (TAC). Ministry of Health directorate of clinical ser Health workers Local experts &Patient groups	Adapted clinical protocols algorithms for hypert diabetes and other cardiome complications to the Zasettings.				
ii. Strengthened diagnostic capacity for decentralized monitoring of haemoglobin A1c, cholesterol, and albumin:creatinine ratio Integrate POC diagnostics or other streamlined at health facility level to enable decentralized ar shifted monitoring of NCDs/ cardiovascular risk facility.		Introduction of point-of-care monitoring or other streadiagnostics at pilot sites Zambia				

iii. Adapt local electronic NCD clinical data collection and decision support tool We will adapt the local EMR (SMARTCARE), a fully integrated electronic health record system, but mainly used for HIV care. We will adapt SMARTCARE to include data collection fields and clinical decision support prompts for NPHWs NCDs and other cardiometabolic complications.	Project TAC. MOH directorate of services Health workers Local experts Patient groups	SMARTCARE Module integrates HIV and NCDs an cardiometabolic complications

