To confirm semantic equivalence, two trilingual (English, Bemba, Nyanja) study staff will back translate WHOQOL-HIV BREF items into English from Nyanja and Bemba. A consensus discussion will then be held between the translators and the MPIs to discuss difficult items with questionable clarity, which will then be resolved by consensus and the WHOQOL-HIV BREF revised accordingly. The final version for assessing known group validity will be called "WHOQOL-HIV-BREF-Zam."

Preparation of the SmartCare NCD module

We will work with a CIDRZ program developer hired by the study team, and with the stewards of the national EMR, SmartCare, which comprise CIDRZ, MOH, CDC/PEPFAR, and BroadReach, to adapt SmartCare to include an NCD module and automatic decision-support prompts for non-physician health workers. We envision that this may include a rather simple adaptation of an existing "outpatient department" module already available in SmartCare.

We will test this adapted version of SmartCare using an innovative approach known as "theatre testing". Theatre testing is a visual consultative process for obtaining rapid feedback on a new service or product from end-users. For this non-human subjects research component, we will use a voluntary sign-up sheet posted at health facility-level to invite ~10-15 adapted NCD SmartCare module end users, including a mix of NPHWs, from CIDRZ-supported sites to observe a demonstration of the module in action and/or use the module themselves. As this will be a convenience sample of SmartCare end users, we cannot exclude the possibility of selection bias among volunteers who agree to participate in theatre testing. However, since the intention of theatre testing is to improve the quality of the NCD module for local implementation, and not to create generalizable knowledge, we do not consider this a substantive methodological limitation. Following the theatre testing, a brief questionnaire (Appendix D. ii) will be administered to obtain feedback on the module that will feature the simple 12-item implementation survey (incorporating empirically supported measures for acceptability, feasibility, and appropriateness) mentioned above, among other implementation-relevant items ⁹⁸. Data from the theatre testing surveys will be summarized using descriptive statistics, and the results used to further refine and finalize the SmartCare module in advance of the pilot in objective #2.

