By completing specific objective #1, we will be fully prepared for TASKPEN pilot testing, having ready an adapted version of TASKPEN that includes all the essential implementation strategies necessary to overcome barriers to HIV-NCD integration in routine care settings. While the peripheral elements and implementation strategies used to introduce TASKPEN may undergo adaptation under specific objective #1, it is important to note that the 5 core, evidence-based components outlined in Table 1 and proposed for this pilot will not substantively change. Under specific objective #2, we will launch the TASKPEN pilot and fully task-shift our intervention to NPHWs and integrate it within the PEPFAR-supported HIV service delivery platform. Concurrently with implementation, during the pilot we will identify facilitators and barriers to TASKPEN introduction, assess preliminary implementation outcomes and patient and provider preferences related to integrated management of cardio-metabolic complications for PLHIV, ascertain early clinical outcomes for patients before and after TASKPEN piloting, and collect formative costing data.

b. Study design

For this objective, we will conduct a quasiexperimental "mini" cross-sectional stepped-wedge study at the 2 pilot sites employing a mixed methods approach. First, at the two pilot sites (i.e. A and B), we will conduct a baseline assessment of select outcomes for PLHIV receiving the existing standard of care. This will involve conducting a brief biobehavioural survey or "patient survey" among a consecutive sample of ~376 adult PLHIV presenting for routine HIV services at the two sites (i.e., ~188 PLHIV per site, see Sample Size and Statistical Power below). After this first patient survey, one randomly selected facility (i.e. cluster) will be switched to the full TASKPEN intervention. The patient survey will be repeated again with another ~376 adult PLHIV after ~3 months at both sites before switching the second site to the full TASKPEN intervention. After switching the second

Figure: Study schematic with "mini" stepped wedge and nested cohort.

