site, both pilot sites A and B will implement the full TASKPEN intervention for another ~3 months after which time a third and final "end line" patient survey will be conducted. Survey data will be used to estimate the pilot effect size of the TASKPEN intervention to aid in planning a future larger trial and to measure WHO PEN process indicators for all PLHIV in care who accessed routine health services during the pilot period.

Complementing the baseline, midline, and endline patient surveys will be a "nested cohort" of PLHIV with cardio-metabolic comorbidities enrolled at both sites beginning at baseline. At each site, we will enrol a subset of ~100 baseline survey participants (i.e., ~200 total) found to have at least one cardio-metabolic complication or risk factor (see below) on the baseline survey. We will then follow these nested cohort participants longitudinally for ~9 months at site A and site B. A nested cohort sample size

TASKPEN Study

of 200 PLHIV was selected to represent about 50% of all baseline survey participants who are estimated to have a cardiometabolic co-morbidity at each site (i.e., ~188 PLHIV in care per site who complete a baseline survey x ~50% of survey participants with hypertension, diabetes, and/or dyslipidaemia = ~100 participants per site), consistent with estimates for the prevalence of cardiometabolic comorbidities among PLHIV in Lusaka, Zambia. Moreover, the nested cohort sample size of ~200 total participants (~100 per site) is intended to assess the feasibility of the intervention and longitudinal follow up of study participants to inform a future larger trial; it is not intended to test a hypothesis *a priori*. By enrolling a nested cohort, we can use their data to enrich inferences made from the cross-sectional surveys and will be able to make more granular comparisons between and within sites (i.e. with an external and internal comparator group, respectively).

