For the cross-sectional patient surveys, we will survey a consecutive sample of 188 eligible patients in care at each clinic at each of the 3-time points (i.e., baseline, midline, and end-line) using a stepped-wedge cluster-randomized design. Applying this design with a sample of 2 clusters (i.e., sites), 3 survey time points, 2 steps, 1 cluster switching from control to intervention at each step, and an average of 564 subjects per cluster (i.e., 188 participants per cluster per period) achieves 80% power to detect a risk ratio of 1.25 (for the risk of dual HIV/NCD control during the intervention period compared to the control period) at the 0.05 significance level with an inter-class correlation coefficient of 0.25. We assumed that

the proportion of participants achieving dual HIV/NCD control is 0.75 under the alternative hypothesis, and 0.6 under the null hypothesis, and used the two-sided Wald Z-Test as the test statistic. Based on the above calculation, we will survey 564 eligible patients at each clinic across the 3-time points (i.e., 3*188=564 eligible patients) to achieve **a total sample size of 1128 participants** for the mini stepped-wedge. It is important to note that participants previously surveyed will not be eligible for subsequent surveys—i.e., once interviewed, a patient should not be eligible for interview in subsequent surveys unless they are part of the nestd cohort. Finally, as part of the baseline, midline, and endline cross-sectional surveys, we will review de-identified routine data for all PLHIV in care at the study sites during the study period to estimate HIV viral load completeness, NCD-variable data completeness (e.g., routine weight and blood pressure measurements), and performance on WHO PEN indicators in the routine medical record.

For the nested cohort component, the total sample size of ~200 participants was selected for operational feasibility and to assess our ability to collect longitudinal cardio-metabolic data, but does not involve *a priori* hypothesis testing.

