For nested cohort participants, study staff will ask them to provide locator information and to complete the midline and endline surveys (shortly after their routine HIV care visits) as part of their ~4 scheduled study follow up visits. Similar handling of abnormal vitals signs and lab testing values will be offered to nested cohort participants as patient survey participants. In addition, we will administer the brief

WHOQOL-HIV-BREF-Zam instrument and the discrete choice experiment questionnaire one time each during one of their ~4 follow up visits. Cohort enrolment will stop when the target number is reached. Finally, we will review cohort participants' HIV and NCD clinical data using a minimally sufficient set of identifying variables (i.e. first name, surname, date of birth, and SmartCare ART number) to follow them longitudinally in the routine medical record. To this end, we will abstract data from existing paper-based patient charts and MOH registers, as well as the electronic SmartCare EMR and LMIS systems to: 1) assess HIV and NCD outcomes (e.g., viral load); 2) evaluate WHO PEN outcome indicators of interest (e.g. proportion of PLHIV routinely screened for hypertension); and 3) monitor for efficient collection of routine data, including routine laboratory test results (e.g. viral load).

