Using baseline, midline, and endline patient survey data and routine EMR data, we will assess the implementation outcomes described in Table 6. We will calculate standardized scores for validated instruments in our implementation survey. Comparisons of proportions for the aforementioned implementation outcomes will be done by calculating prevalence ratios and associated 95% confidence intervals as appropriate. Comparisons of continuous outcomes will be done by the Z-test/ 2-sample T-test or the Wilcoxon Rank-Sum test as appropriate.

To understand patient-level outcome measures of **disease control, retention**, **adherence**, and **viral suppression**, we will analyse data from the patient surveys. We will estimate **dual disease control** as the proportion of participants in the intervention and control periods who have a HIV viral load <200 copies/ml and do not have uncontrolled systolic hypertension, diabetes, and/or dyslipidaemia. We will calculate **retention** as the proportion of participants considered to be consistently engaged in care at 6 months according to the national HIV treatment program definition (e.g., without evidence of death, default, or loss to follow up defined as ≥30 days having elapsed since a missed pharmacy refill/ clinic visit). We will measure **adherence** in the nested cohort by reviewing pharmacy records at 6 months to calculate the medication possession ratio (MPR) over that time frame for anti-hypertensive, diabetes, and dyslipidaemia medications, as well as antiretroviral therapy. We will calculate **viral suppression** as the proportion of survey participants meeting established thresholds of suppression (e.g., viral load <1,000 copies/ml or <200 copies/ml) at 6 months following ART initiation and/or study enrolment. To compare outcome measures, we will report differences and ratios with accompanying 95% confidence intervals. We will compute variance for differences and ratios using the sandwich variance estimator or appropriate resampling approaches to account for the clustered nature of the data by site.

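### WHO PEN process indicators are read from a routine record that TASKPEN itself alters, so a rise after a site's switch can be better recording, and the record alone cannot tell that from better care

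*Combined protocol and SAP*

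**What the plan says.** - **Source of the indicators.** Specific Objective #2, section d.v, adds to each of the three survey rounds a review of de-identified routine data on all PLHIV in care, to estimate data completeness and "performance on WHO PEN indicators in the routine medical record". Section e.iii, on abstracting the records of nested-cohort participants, gives the example: staff will "evaluate WHO PEN outcome indicators of interest (e.g. proportion of PLHIV routinely screened for hypertension").
- **A second, different source.** Section b (Study design) says that survey data will be used to "measure WHO PEN process indicators for all PLHIV in care who accessed routine health services during the pilot period".
- **The record is part of the intervention.** Table 2, component iii: "We will adapt SMARTCARE to include data collection fields and clinical decision support prompts for NPHWs". In section b, after the baseline survey, "one randomly selected facility (i.e. cluster) will be switched to the full TASKPEN intervention"; the other site follows after midline.
- **The module is also a measuring tool.** Section 7, objective 1.ii, lists it under the aim to "Prepare data collection tools and methods to enable TASKPEN outcome ascertainment during pilot testing and the follow-on trial".
- **Timing.** Under Specific Objective #1, theatre testing will be used to "further refine and finalize the SmartCare module in advance of the pilot in objective #2". No go-live date by site is given.
- **Analysis.** Section g.i: "Using baseline, midline, and endline patient survey data and routine EMR data, we will assess the implementation outcomes", with prevalence ratios for proportions.

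**The concern.** For a process indicator read from a record, a check that was done but not entered counts as not done. If the fields and prompts arrive at a site when TASKPEN does, the yardstick changes at the same moment as the treatment. A period effect cannot absorb this, because the recording change coincides with the treatment indicator and not with calendar time.

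Real change may arrive at the same moment: component v has community health workers take blood pressure, and prompts may lead staff to do more checks. The record shows the sum of the two changes and cannot divide it.

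Better recording is a legitimate TASKPEN result when reported as recording. The risk is that it is reported as more patients screened. One Objective #1 output is a set of agreed indicators that would justify moving to a larger program. The protocol does not name them; if record-based WHO PEN indicators are among them, documentation could pass for care.

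**Working it through.** **The plan's own figures.** No figure is stated for the WHO PEN indicators. The only design calculation, 80% power for dual control with 188 patients per site per round, reproduces: the Hussey-Hughes stepped-wedge variance with total variance 0.6 × 0.4 and ICC 0.25 gives 80.03%. It does not bear on this point.

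**Inputs from Table 4** (headings broken; second documentation column assumed to be blood pressure):
- George: 38/8785 = 0.43%
- Chilenje: 6484/8083 = 80.2%

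The two tentative pilot sites thus differ by about 80 points in documentation before any intervention.

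**What a pure recording change would do.** Let A be the site that switches first and B the second, with rounds at 0, 3 and 6 months. In a linear model with site effects, time effects and a treatment term, the treatment estimate from the six cell means is

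[A3 − (A0 + A6)/2] − [B3 − (B0 + B6)/2].

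Hold care constant and let the documented share jump by *a* at A's switch and by *b* at B's:
- A part: *a* − *a*/2 = *a*/2
- B part: 0 − *b*/2 = −*b*/2
- Estimate: *a*/2 + *b*/2, the mean of the two sites' recording jumps, whichever site goes first.

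**Numbers put in.** The post-switch levels are assumptions; the documents give none.

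| George rises to | Chilenje stays at 80.2% | Chilenje rises to 90% |
|---|---|---|
| 0.43% (no change) | 0 | +4.9 points |
| 10% | (10 − 0.43)/2 = +4.8 | +9.7 |
| 20% | +9.8 | +14.7 |
| 50% | +24.8 | +29.7 |
| 80% | +39.8 | +44.7 |

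If the module runs at both sites before baseline, *a* = *b* = 0 and the spurious effect is 0.

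**Does section g.i already deal with this?** It plans imputation for measurement error and missing data, and the sensitivity and specificity of routine measures against the nested cohort. Four things limit this:
- The cohort contains only people with a cardio-metabolic condition or risk factor (section d.ii), whereas screening concerns everyone in care.
- It validates disease measures, that is diagnoses and biomarkers. It does not establish whether the clinic carried out a check.
- Accuracy is not to be reported separately for control and intervention periods, which is what would reveal a change in recording.
- The same section also says that missing values will not be imputed.

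Reporting completeness beside performance (section d.v) does not separate them either. For an indicator such as screened for hypertension, the two are nearly the same number.

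**The case against.** The strongest case on the other side has five parts.

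1. **Timing is inferred.** The protocol says only that the module is finalized before the pilot, and lists it as an ascertainment tool. It could run at both sites from baseline. This stands, and it makes the point conditional.
2. **Blood pressure already has a place in the record.** Section d.v treats it as a routine measurement, and Chilenje appears to document it for about 80%. George's 0.43% therefore cannot be put down to a missing field; few checks may be done there, and Table 1 lists lack of vital-sign equipment as a barrier. This also stands. It means that the indicators can rise through recording, not that they must.
3. **Paper sources are abstracted too.** Section e.iii covers charts and registers, so a check on paper could be seen before the switch. This is clearest for the nested cohort. For the all-PLHIV review the protocol names only the routine medical record.
4. **Survey data are named as a source.** True, in section b, but section d.v names the record. The two need reconciling.
5. **No such contrast is planned.** The site-plus-time model is specified for dual control, risk scores and quality of life, and the implementation-outcomes table does not list hypertension screening. This stands, so the figures above are an illustration only.

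A reader might infer that NCD fields are absent in every control period and that a false screening effect is bound to appear. The documents do not support that: no go-live date is stated, and the blood pressure field already exists.

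**Conclusion.** The point holds in conditional form. The module is both part of the intervention and part of the measurement. If it goes live at the switch, a change in a record-based process indicator cannot be attributed to care, and nothing in the plan separates the two.

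The possible size runs from zero (no recording change, or the module live at both sites before baseline) to about +40 points (George's documented share at 80%, Chilenje's recording and all care unchanged). It would reach about +45 points if Chilenje also rose to 90%. This rests on the assumed reading of the Table 4 column, on assumed post-switch levels, on the tentative choice of sites, and on a linear contrast that the plan does not specify for these indicators.

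A reader might extend the concern to the pilot's effect estimate. That does not follow: dual control is compared in the patient surveys, where study staff measure blood pressure, glucose and lipids in the same way at each round. Nor do the documents name record-based indicators as the criterion for the larger trial.

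**What to change.** 1. Reconcile section b with section d.v: estimate WHO PEN process performance from a few items in the patient survey on clinic services received. The survey uses one instrument in all three rounds (section e.v) and is to follow most clinic services (section d.vi). The items must ask about the clinic's checks, not the study's own measurements.
2. Where the record is used, abstract the same paper and electronic sources for surveyed patients in every period.
3. Report the all-PLHIV record-based indicators as documentation outcomes, and state that their change across a switch is not read as a change in care.
4. State the module's go-live date at each site. If it precedes baseline at both, the module-related concern largely falls away.

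The cost is protocol wording, a few survey items, and abstraction limited to at most 1128 surveyed patients (188 × 2 sites × 3 rounds). The price is some self-report error and the loss of the all-PLHIV denominator for the care comparison.
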